14.2 Institutional Review Boards

- 1985 The protocol, informed consent form(s), recruitment materials, and all participant materials will
- be submitted to the IRB for review and approval. Approval of both the protocol and the consent
- 1987 form must be obtained before any participant is enrolled. Any amendment to the protocol will
- require review and approval by the IRB before the changes are implemented to the study. All
- changes to the consent form will be IRB approved; a determination will be made regarding whether
- previously consented participants need to be re-consented.

14.3 Informed Consent Process

14.3.1 Consent Procedures and Documentation

- 1993 Informed consent is a process that is initiated prior to the individual's agreeing to participate in
- the study and continues throughout the individual's study participation. Extensive discussion of
- risks and possible benefits of participation will be provided to the participants and their families.
- 1996 Consent forms will be IRB-approved and the participant will be asked to read and review the
- document. The investigator will explain the research study to the participant and answer any
- 1998 questions that may arise. All participants will receive a verbal explanation in terms suited to
- their comprehension of the purposes, procedures, and potential risks of the study and of their
- 2000 rights as research participants. Participants will have the opportunity to carefully review the
- written consent form and ask questions prior to signing.
- The participants should have the opportunity to discuss the study with their surrogates or think
- about it prior to agreeing to participate. The participant will sign the informed consent document
- prior to any procedures being done specifically for the study. The participants may withdraw
- 2005 consent at any time throughout the course of the trial. A copy of the informed consent document
- will be given to the participants for their records. The rights and welfare of the participants will
- be protected by emphasizing to them that the quality of their medical care will not be adversely
- affected if they decline to participate in this study.

14.3.2 Participant and Data Confidentiality

- 2010 Participant confidentiality is strictly held in trust by the participating investigators, their staff,
- and the sponsor(s) and their agents. This confidentiality is extended to cover testing of
- 2012 biological samples and genetic tests in addition to the clinical information relating to
- 2013 participants. Therefore, the study protocol, documentation, data, and all other information
- 2014 generated will be held in strict confidence. No information concerning the study or the data will
- be released to any unauthorized third party without prior written approval of the sponsor.

2016 The study monitor, other authorized representatives of the sponsor, representatives of the IRB, 2017 regulatory agencies or company supplying study product may inspect all documents and records 2018 required to be maintained by the investigator, including but not limited to, medical records 2019 (office, clinic, or hospital) and pharmacy records for the participants in this study. The clinical 2020 study site will permit access to such records. 2021 The study participant's contact information will be securely stored at each clinical site for internal use during the study. At the end of the study, all records will continue to be kept in a 2022 2023 secure location for as long a period as dictated by the reviewing IRB, institutional policies, or 2024 sponsor requirements. 2025 Study participant research data, which is for purposes of statistical analysis and scientific reporting, 2026 will be transmitted to and stored at the Jaeb Center for Health Research (JCHR). This will not 2027 include the participant's contact or identifying information, unless otherwise specified in the 2028 informed consent form. Rather, individual participants and their research data will be identified 2029 by a unique study identification number. The study data entry and study management systems 2030 used by clinical sites and by JCHR research staff will be secured and password protected. At the 2031 end of the study, all study databases will be de-identified and archived at the JCHR and the 2032 University of Virginia Center for Diabetes Technology.

2034	Chapter 15: Ancillary Study to Test Control-IQ System with Meal
2035	Bolus and Exercise Challenges
2036	15.1 Objective
2037 2038 2039	This Ancillary Study will assess the safety of using the study system during exercise and meal bolus-related challenges. Outcome data are expected to be used to support regulatory filings for the device system.
2040	15.2 Sample Size
2041 2042 2043	Participation in the Ancillary Study will be offered to participants who are currently in the Extension Phase of the main study. The goal for sample size is to have 30-40 individuals participate in the Ancillary Study.
2044	15.3 Eligibility Criteria
2045 2046 2047	Participants must be currently in the Extension Phase of the main study, with at least 2 weeks and no more than 11 weeks completed to ensure sufficient comfort with the study pump and sufficient time to complete the protocol below.
2048 2049	Inclusion in the Ancillary Study requires investigator judgment that it is safe for the individual to participate.
2050	15.4 Study Procedures
2051 2052	On the day of enrollment into the Ancillary Study, informed consent will be obtained from interested participants, and eligibility will be verified.
2053 2054 2055	A paper logbook will be provided to participants that includes a page to record details about each challenge and procedural instructions about how participants will conduct these challenges. This material will be reviewed with each participant.
2056 2057 2058 2059 2060 2061	During home use, each participant will perform 3 exercise and meal bolus-related challenges (details below) appropriate for the age of the participant. Each challenge will be separated from the other challenges by at least 48 hours. Before starting each challenge, caregivers of the child must assure the child has a working CGM and Control-IQ is active. If activity is paused during an exercise-related challenge, the challenge may be continued to allow for continuation of the activity if the participant is able and willing to continue.
2062 2063	Participants will receive a guidance document for performing the challenges that includes the following safety mitigations:
2064 2065 2066	• The participant's parent or guardian must remain with the child at all times and monitor CGM readings frequently during and for at least two hours after completion of each challenge.

- The hyperglycemia safety protocol described in section 8.2.4 will be followed during each challenge.
 - The parent/guardian must have an on-call phone number for the study team prior to initiation of each challenge.
 - CGM glucose must be ≥120 mg/dL prior to initiation of each exercise-related challenge.
 - Exercise may not be initiated during an exercise-related challenge if the CGM trend arrows on the study insulin pump indicate Falling glucose (down arrow) or Rapidly Falling glucose (double down arrow).
 - Snacks and glucagon must be available for use during and after each exercise-related challenge.
 - Control-IQ exercise activity mode must be activated at least 30 minutes prior to the start of exercise during each exercise-related challenge and kept active for at least 30 minutes after completion of the exercise period.
 - Additional carbohydrate may be given as needed at the start of, during, or after each exercise-related challenge.
 - The temporary basal rate feature of the study pump may be used if desired to reduce insulin delivery during the exercise period of each exercise-related challenge.
 - Fingersticks will be performed for any low CGM value <70 mg/dL, and any exercise should be stopped if BG is confirmed <70 mg/dL. Exercise may be stopped for concerns for CGM decreasing at any time, even if CGM is >70 mg/dL.
 - A parent/guardian will sleep in the same home as the child overnight and closely monitor CGM readings following days when one of the challenges was performed.
- 2090 Contact with the study investigator may be initiated at any time.
- 2091 Challenge Details:
- 2092 Missed Meal Bolus Challenge: Participants will skip their meal bolus for an afternoon meal of
- at least 20 grams carbohydrate. The meal timing and carb amount and any additional snacks
- 2094 given will be recorded on a study exercise log. Additional insulin boluses may be given for
- 2095 hyperglycemia as needed. The hyperglycemia safety protocol described in section 8.2.4 will be
- 2096 followed.

2069

2070

2071

2072

2073

2074

2075

2076

2077

2078

2079

2080

2081

2082

2083

2084

2085

2086

2087

2088

- Full Meal Bolus Plus Exercise Challenge: Participants will receive a full meal bolus for an
- afternoon meal of at least 20 grams carbohydrate. The pump's Exercise Activity setting will be
- 2099 turned on upon completion of the meal. Beginning 30 minutes after completion of the meal, a
- 2100 parent/guardian will try to keep the child physically active (walking, running, playing) for at
- 2101 least 30 minutes if possible, or longer if desired. This can be mixed with mild activity. The meal
- 2102 timing and carb amount, the actual stop and start time of exercise, any associated hypoglycemia
- treatments, and any additional snacks given will be recorded on a study exercise log.

- 2104 Exercise Challenge: At least 2 hours after the child finishes an afternoon meal, a
- 2105 parent/guardian will try to keep the child physically active (walking, running, playing) for at
- least 30 minutes if possible, or longer if desired. This can be mixed with mild activity. The 2106
- 2107 pump's Exercise Activity setting will be turned on 90 minutes after completion of the meal. The
- meal timing and carb amount of the last meal prior to exercise, the actual start and stop time of 2108
- 2109 exercise, any associated hypoglycemia treatments, and any additional snacks given will be
- 2110 recorded on a study exercise log.
- 2111 A challenge may be stopped for any reason, including participant non-cooperation, or concern
- 2112 for hypoglycemia, or repeated hypoglycemia.
- 2113 15.5 Outcomes and Analysis Plan
- 2114 A separate statistical analysis plan will be written for the Ancillary Study.
- 2115 Outcomes will include the following:
- 2116 **Key Safety Outcomes:**
- 2117 Severe hypoglycemia
- 2118 • Other adverse events
- 2119 All adverse events will be listed. Listings will include Participant ID, the event, whether the
- 2120 event was serious, whether the event was related to the study device, the event outcome, and a
- 2121 description of the event.
- 2123 **Other Outcomes**

- 2124 CGM-measured % <54 mg/dL overnight (all challenge types)
- 2125 • CGM-measured % <70 mg/dL overnight (all challenge types)
- 2126 • CGM-measured % >180 mg/dL overnight (all challenge types)
- 2127 CGM-measured % <54 mg/dL during the two hours immediately following the start of exercise for each exercise-related challenge 2128
- 2129 • CGM-measured % <70 mg/dL during the two hours immediately following the start of 2130 exercise for each exercise-related challenge
- 2131 • CGM-measured % >180 mg/dL during the four hours following the announced meal, or 2132 until the next meal bolus is given, for the missed meal bolus challenge
- 2133 CGM-measured % >300 mg/dL during the four hours following the announced meal, or 2134 until the next meal bolus is given, for the missed meal bolus challenge
- 2135 The percentage of time spent below 54 mg/dL from 10 PM - 5.59 AM the night of an exercise
- 2136 challenge will be compared with percentage of time spent below 54 mg/dL the previous night
- using a linear mixed effects regression model. A point estimate, 95% confidence interval and 2137
- 2138 two-sided p-value will be reported for the challenge effect based on the linear regression model
- 2139 and a 5% level will be used to declare statistical significance. Residual values will be examined
- 2140 for an approximate normal distribution. If values are highly skewed, then robust regression using
- 2141 M-estimation will be used instead. Analysis of the percentage of time spent below 70 mg/dL 10

2142 PM – 5:59 AM the night of an exercise challenge will be performed in the same manner.

2143

- 2144 The percentage of time spent above 180 mg/dL from 10 PM - 5.59 AM the night of a missed
- meal bolus challenge will be compared with percentage of time spent above 180 mg/dL the 2145
- 2146 previous night using a linear mixed effects regression model. A point estimate, 95% confidence
- 2147 interval and two-sided p-value will be reported for the challenge effect based on the linear
- 2148 regression model and a 5% level will be used to declare statistical significance. Residual values
- will be examined for an approximate normal distribution. If values are highly skewed, then 2149
- 2150 robust regression using M-estimation will be used instead. Analysis of the percentage of time
- 2151 spent above 300 mg/dL 10 PM – 5:59 AM the night of a missed meal bolus challenge will be
- performed in the same manner. 2152

2153

- 2154 CGM-measured % <54 mg/dL during the two hours immediately following the start of exercise
- 2155 for each exercise challenge will be compared between the two exercise challenge groups using a
- 2156 paired t-test. CGM-measured % <70 mg/dL during this same period will be analyzed in the same
- 2157 manner.

- 2159 For each challenge type, the mean, standard deviation, and range will be given for the outcomes
- 2160 listed above relevant to the challenge type. Summary statistics for the overnight periods
- preceding the challenges will be presented with summary statistics for each challenge type. 2161
- 2162 **Safety Monitoring**
- 2163 Safety oversight will be the same as for the main study, as described in Chapter 10:.

Chapter 16: References

- 2164
- 2165 1. Brown S, Kovatchev B, Raghinaru D, Lum JW, Buckingham BA, Kudva YC, Laffel LM,
- Levy CJ, Pinsker JE, Wadwa RP, Dassau E, Doyle FJ, Anderson SM, Church MM, Dadlani

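### The ancillary study tests one exercise challenge against the other within child, but the protocol does not randomize or balance their order, so a change in caregiver behaviour could bias the comparison

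*Protocol*

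**What the plan says.** Protocol section 15.4 describes three home challenges: a missed meal bolus, a full meal bolus followed by exercise, and exercise alone. The wording is that "each participant will perform 3 exercise and meal bolus-related challenges (details below) appropriate for the age of the participant". The only timing rule between them is "Each challenge will be separated from the other challenges by at least 48 hours". No order is given, whether fixed, randomized or counterbalanced.

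The two exercise challenges differ mainly in when exercise starts. In one it begins 30 minutes after a fully bolused afternoon meal. In the other it begins two hours or more after an afternoon meal. In both, caregivers must watch the CGM closely and have discretion: "Additional carbohydrate may be given as needed at the start of, during, or after each exercise-related challenge". They may also use a temporary basal rate or stop exercise if the CGM is falling.

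Section 15.5 plans a formal test. The % <54 mg/dL in the two hours from the start of exercise "will be compared between the two exercise challenge groups using a" "paired t-test. CGM-measured % <70 mg/dL during this same period will be analyzed in the same" manner. No order or period term is mentioned.

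On size, section 15.2 says only that "The goal for sample size is to have 30-40 individuals participate in the Ancillary Study". Section 15.5 also promises a separate SAP for the ancillary study. That SAP is not among the documents, and the SAP supplied covers only the randomized phase.

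**The concern.** A paired test removes stable differences between children. It does not remove a change between a child's first and second exercise challenge. A parent who saw glucose fall the first time may feed earlier, use the temporary basal rate or stop sooner the second time, and each of these acts directly on time below range in the two-hour window. The 48-hour gap limits glucose carry-over but not what a caregiver remembers.

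If most families do the same exercise challenge first, this change falls mainly on one side of the paired difference and would be read as a difference between the challenges. This is the only planned test of one challenge against another; the other formal tests compare a challenge night with the night before. Section 15.1 expects the ancillary data to support regulatory filings.

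**Working it through.** **The plan's own figure.** The only figure is the 30–40 participants in section 15.2. No SD, effect size or power comes with it, so it cannot be reproduced.

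**Inputs**
- From the protocol: 30–40 children (35 pairs used below) and a paired t-test within child.
- Significance level: two-sided 5%. Section 15.5 states this for the overnight models ("and a 5% level will be used to declare statistical significance") and does not restate it for the paired t-test. The same level is assumed.
- Assumed, with no source in the documents: the SD of the paired difference in % <70 (8 points, also 12), the order effect L (0.5, 1 and 2 points), and the share q of children who do one given exercise challenge first (60%, 80%, 100%).

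**Bias.** Let L be the fall in % <70 from the first to the second exercise challenge, the same whichever comes first. Children in one order contribute +L to the mean paired difference and the rest contribute −L:

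bias = qL − (1 − q)L = (2q − 1)L

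This is zero when q = 0.5 or L = 0.

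**Standard error.** SE = 8/√35 = 1.35 points. With an SD of 12, SE = 12/√35 = 2.03.

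**Type I error when the challenges do not differ** (normal approximation): P(|Z + bias/SE| > 1.96).

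| SD | L (points) | q | Bias (points) | Bias/SE | Type I error |
|---|---|---|---|---|---|
| 8 | 0.5 | 80% | 0.3 | 0.22 | 0.056 |
| 8 | 1 | 80% | 0.6 | 0.44 | 0.073 |
| 8 | 2 | 60% | 0.4 | 0.30 | 0.060 |
| 8 | 2 | 80% | 1.2 | 0.89 | 0.144 |
| 8 | 2 | 100% | 2.0 | 1.48 | 0.316 |
| 12 | 2 | 80% | 1.2 | 0.59 | 0.091 |

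**Check by simulation of the t-test itself** (40,000 runs, no true difference, L in SDs of the paired difference). Two points at an SD of 8 is 2/8 = 0.25 SD.

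| L | Order | n = 30 | n = 40 |
|---|---|---|---|
| 0.25 SD | all the same | 0.263 | 0.334 |
| 0.25 SD | 22 of 30, or 30 of 40 | 0.090 | 0.108 |
| 0.25 SD | exactly half and half | 0.043 | 0.044 |
| 0.25 SD | randomized per child | 0.050 | 0.049 |

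The value of 0.316 for 35 pairs lies between 0.263 and 0.334, as it should. With an order term in the model, the error was 0.049–0.052 in every simulated case where both orders occurred. If every child follows the same order, that model cannot be fitted.

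**Scale.** The t-test has 80% power for a true difference of 0.53 SD at n = 30 and 0.455 SD at n = 40. At an SD of 8 these are 0.53 × 8 = 4.2 and 0.455 × 8 = 3.6 points. A 2-point order effect is therefore about half of what the test can detect.

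No separate SD was assumed for % <54. The error rates depend only on L/SD, n and q, so the same rates apply wherever L/SD is the same.

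**The case against.** **Silence is not free choice.** A reader might infer that families pick the sequence themselves. The documents do not say so. Section 15.4 mentions a logbook with procedural instructions, reviewed with each participant, and that unseen material could set or vary the order. This stands: the protocol shows only that order is not controlled in its own text.

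**The bias is conditional.** A reader might infer that the comparison cannot separate challenge from practice. That goes too far, because bias needs both a learning effect and unbalanced orders. Learning may also be small. Children join after two weeks or more in the Extension Phase, those from the CLC arm have used the system longer, and exercise cannot start unless CGM level and trend conditions are met. This stands too. Several rows of the first table leave the error near 5%.

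**The contrast is not a pure meal-bolus effect.** A reader might label it so. Both challenges follow a meal, and the protocol does not say that the bolus is left out of the exercise-only challenge. The contrast is mainly the time from meal to exercise. Discretionary carbohydrate can also differ between challenges whatever the order, and randomizing order would not change that.

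**The separate SAP may cover it.** It could add an order term, and the logbook page for each challenge may let the order be recovered. But an analysis plan cannot randomize the order, and an order term is of no use if every child follows one sequence. On this part the objection fails.

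**Low stakes.** The two-hour measures are listed under Other Outcomes. The key safety outcomes, severe hypoglycemia and other adverse events, do not depend on this test. This is correct and limits the weight of the point.

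**Conclusion.** The point holds as a cheap improvement to the design. The protocol plans a formal within-child test and does not randomize or balance the order of what it compares. Bias is possible, not established.

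Under the stated assumptions for % <70, the type I error runs from little above the nominal 5% to about 32%. The top of that range needs a 2-point order effect and every child in the same order. The SD, the order effect and the order share are all assumptions, so none of these figures is an estimate for this trial. The calculation also takes the order effect to be the same whichever exercise challenge comes first.

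Nothing here bears on the randomized comparison, its primary outcome or its hierarchical tests.

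**What to change.** - **Section 15.4:** assign each family a pre-generated, randomized order of the three challenges, balanced so that each exercise challenge comes first equally often. Three challenges have six possible orders, and each exercise challenge precedes the other in three of them, so equal use of the six achieves this. Keep every safety condition and the 48-hour gap as they are. Record the assigned order, the actual order and the dates.
- **Section 15.5 and the ancillary SAP:** add an order (period) term to the two-hour comparison for % <54 and % <70. Balance alone removes the bias, but the plain t-test then becomes somewhat conservative (0.043–0.044 in the simulation). The order term restores the nominal level.
- **If order is not randomized,** or the challenges have already been done: tabulate the order actually followed and present the two-hour comparison as descriptive, without a claim of significance.

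The cost is a sequence list and a short amendment, with no new procedure. The order and dates may already be recoverable from the logbook. The downside is slightly less scheduling freedom for families.

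### Ancillary Study: each challenge night is compared with only the one preceding night, although further reference nights on the same system are already collected and would tighten the overnight contrasts at almost no cost

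*Protocol*

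**What the plan says.** Protocol section 15.5 compares the period 10 PM to 5:59 AM after a challenge with the same period one night earlier. For % <54 mg/dL the exercise "challenge will be compared with percentage of time spent below 54 mg/dL the previous night"; % <70 mg/dL is handled in the same way. For the other challenge type, the missed "meal bolus challenge will be compared with percentage of time spent above 180 mg/dL the" previous night, and % >300 mg/dL follows the same pattern. The descriptive summaries likewise use only the overnight periods that precede the challenges.

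The analysis is a linear mixed effects model, with M-estimation as the fallback if residuals are highly skewed. A "two-sided p-value will be reported for the challenge effect based on the linear regression model", and significance is judged at the 5% level. No covariance structure is stated, and no reason is given for using a single reference night.

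On size, section 15.2 says only: "The goal for sample size is to have 30-40 individuals participate in the Ancillary Study". No SD, effect size or power accompanies it. On eligibility, section 15.3 admits children in the Extension Phase "with at least 2 weeks and no more than 11 weeks completed". Section 12.17.1 removes from the Extension Phase analysis only the data from the start of a challenge to 5:59 AM the next morning, so all other nights are kept. Section 15.5 defers detail to a separate ancillary SAP, and the SAP supplied (section 17.2) says the same.

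**The concern.** A single 8-hour night is a noisy reference for a quantity such as % <54 mg/dL. In a within-child contrast of one night against one night, half of the variance comes from the reference. With 30-40 children, and no easy way to add more, that is precision given up while usable nights sit in the same database.

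The purpose of the Ancillary Study makes this worth attention. Section 15.1 says that it assesses safety during challenges and that the data are expected to support regulatory filings. When the question is harm, a wide interval and a non-significant result look reassuring but may say little about whether overnight hypoglycemia rose.

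**Working it through.** **Inputs from the protocol.** One reference night per challenge night (15.5); 30 to 40 children (15.2); two-sided 5% level (15.5); three challenges per child at least 48 hours apart (15.4). The plan states no precision or power for this study, so there is no figure to reproduce.

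**Assumptions.** The night-to-night SD within a child, s, is not given, so results are in units of s. The correlation r between adjacent nights is not given; it is taken as AR(1) and varied from 0 to 0.5.

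**Independent nights.** The variance of challenge night minus the mean of m reference nights, per child, is s²(1 + 1/m); between-child variance cancels.
- m = 1: 2.000 s².
- m = 7: 1.143 s². SE ratio = √(1.143/2.000) = 0.756, a 24% reduction. The variance ratio 2.000/1.143 = 1.75 is the equivalent multiple of children.
- m = 5: √(1.200/2.000) = 0.775. m = 3: √(1.333/2.000) = 0.816.

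The 95% half-width is 1.960 × √((1 + 1/m)/N), and the difference detectable with 80% power is (1.960 + 0.842) × √((1 + 1/m)/N), both in units of s:

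| N | Half-width, m = 1 | Half-width, m = 7 | Detectable, m = 1 | Detectable, m = 7 |
|---|---|---|---|---|
| 30 | 0.506 | 0.383 | 0.723 | 0.547 |
| 40 | 0.438 | 0.331 | 0.626 | 0.474 |

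**Correlated nights.** With one adjacent reference night the variance is 2(1 − r)s². With seven nights and a model that represents the correlation (optimal weights), it is s²[(1 − r²) + (1 − r)²(1 + r)/(7 − 5r)]. At r = 0.5 this is 0.750 + 0.375/4.5 = 0.833, against 1.000 for one night, so the SE ratio is √0.833 = 0.913. An equally weighted seven-night mean behaves differently:

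| r | One night | Seven, modelled | SE ratio | Seven, equal weights | SE ratio |
|---|---|---|---|---|---|
| 0 | 2.000 | 1.143 | 0.756 | 1.143 | 0.756 |
| 0.2 | 1.600 | 1.088 | 0.825 | 1.130 | 0.840 |
| 0.4 | 1.200 | 0.941 | 0.885 | 1.098 | 0.957 |
| 0.5 | 1.000 | 0.833 | 0.913 | 1.064 | 1.032 |

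With the correlation modelled, the gain runs from 24% down to 9%. With equal weights it has gone by r = 0.5.

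**Challenge effect that varies between children.** If its variance is h·s², the SE ratio at r = 0 is √((1 + 1/7 + h)/(2 + h)).
- h = 0.5: √(1.643/2.5) = 0.811.
- h = 2: √(3.143/4) = 0.886.

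The gain is then about 19% to 11%.

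**Shared reference nights.** If the two exercise-related challenges are pooled and share the same seven reference nights, the comparison is √((1/2 + 1/7)/(1/2 + 1/2)) = 0.802, a 20% gain at r = 0.

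**The case against.** The previous night is a defensible matched control. It is the closest in time and therefore in pump settings, which may be re-optimised during the Extension Phase (6.3.7), and the 48-hour spacing keeps it from being a challenge night itself. Widening the window trades some of that matching for precision. This stands as a small cost, and it is why the previous-night contrast should be kept.

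The 24% figure is a best case. It needs independent nights and a common challenge effect, and two earlier challenges in the same week can leave five usable nights instead of seven. This stands. It is also true that adding nights without stating a correlation structure could lose the gain or misstate the SE, so the model needs an explicit term.

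The ancillary SAP was not among the documents and may already settle the reference period. This stands too; the protocol text alone does not settle it.

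Two stronger readings are tempting and are not supported:
- A reader might infer that the night before a challenge is biased toward calm nights because families pick the day with the investigator's agreement. Section 15.3 requires investigator judgment only for entry to the Ancillary Study. Nothing in 15.4 requires approval of a challenge day, and the CGM conditions there apply when an exercise-related challenge starts, not to the previous night.
- A reader might infer that every child has two weeks of nights on the same system. Chapter 6 allows the updated pump to be deferred by up to 2 weeks while the child stays on the RCT-period treatment. On a literal reading, such a child could have completed 2 Extension Phase weeks with few nights on the updated pump.

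**Conclusion.** The point holds as an inexpensive improvement in precision, not as an error that undermines the study. Seven reference nights would cut the SE of the overnight contrasts by about 24% at r = 0 and 9% at r = 0.5 if serial correlation is modelled, and by about 11% to 19% at r = 0 if the challenge-effect variance is 2 to 0.5 times s². These figures rest on an assumed AR(1) correlation, complete nights and the linear mixed model; if the M-estimation fallback is used they are only a guide.

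A reader might take this as a flaw in the main safety conclusion of the Ancillary Study. It is not. Section 15.5 lists these CGM contrasts under other outcomes; the key safety outcomes are severe hypoglycemia and other adverse events, which are listed event by event and do not depend on the reference night. The randomized comparison is untouched.

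**What to change.** In section 15.5, or in the ancillary SAP if it does not already do so:
- Define the reference as all available non-challenge nights (10 PM to 5:59 AM) on the updated system in the 7 days before each challenge, leaving out any night that follows another challenge.
- Enter each night as a repeated measure in the planned linear mixed model, with challenge night as the effect of interest, a random effect for child, and a serial-correlation term such as AR(1) indexed by calendar night, so that gaps left by excluded nights are respected.
- Use whatever eligible nights a child has if pump initiation was deferred. Even three nights give an SE ratio of 0.816 under independence.
- Keep the previous-night contrast as a sensitivity analysis.

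The cost is a wording change and some extra data handling. No new data, visits or participants are needed. The downside is that some reference nights are up to a week older, when pump settings may have differed slightly; the retained previous-night contrast shows whether that matters.
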